5.4. Selection of Study Population

5.4.1. Inclusion Criteria

All Subjects

Subjects must fulfill all of the following inclusion criteria to be eligible for participation in the study:

1. Participants legally competent to sign and give informed consent or (for adolescents) assent.
2. Males and females ages 9 years and older (inclusive) at the time of consent.
3. Females of childbearing potential (FOCBP) must have a negative urine pregnancy test at all study visits. In addition, sexually active FOCBP must agree to use at least one form of an acceptable effective contraception throughout the trial. Acceptable effective forms of contraception may include: oral/implant/injectable/transdermal contraceptives, intrauterine device, or partner's vasectomy. If barrier methods are used (e.g., condom with spermicide, diaphragm with spermicide), then 2 forms of contraception are required. The use of abstinence as a contraceptive measure is acceptable as long as this is a consistent part of a lifestyle choice and a backup method has been identified if the subject becomes sexually active.
4. Female of non-childbearing potential must be either pre-menarchal or post-menopausal women with spontaneous amenorrhea for at least 12 months or have undergone surgical sterilization (permanent sterilization methods include hysterectomy, bilateral oophorectomy, hysteroscopic sterilization, bilateral tubal ligation or bilateral salpingectomy).

Cohort 1 Only

5. Subjects with seborrheic dermatitis who met eligibility criteria for a prior ARQ-154 study, successfully completed a prior ARQ-154 study through the final visit and are able to immediately enroll into this long-term safety study on the final visit of a previous ARQ-154 study.

Cohort 2 Only

For subjects that have not participated in a prior ARQ-154 study:

6. Clinical diagnosis of seborrheic dermatitis of at least 3 months duration as determined by the Investigator. Stable disease for the past 4 weeks.
7. Seborrheic dermatitis of the scalp and/or face and/or trunk and/or intertriginous areas up to $\leq 20\%$ BSA involvement.
8. An Investigator Global Assessment (IGA) of disease severity of at least Moderate ('3') at Day 1.
9. Overall Assessment of Erythema and Overall Assessment of Scaling scores of at least Moderate ('2') at Day 1.

For subjects that have completed a prior ARQ-154 study prior to initiation of the current ARQ-154-214 study:

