6.2.4. Body Surface Area (BSA)

BSA Assessments will be performed at the timepoints outlined in the Schedule of Visits and Assessments ([Section 1.3](#)).

The BSA affected by seborrheic dermatitis will be determined by the subject's hand method, where the subject's hand (including fingers) surface area is assumed to equal 1% of body surface area (BSA).

[figure not shown]

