2.2.1.3. Other Secondary Efficacy Endpoints

Other secondary efficacy endpoints of this study include the following:

- Change and percent change in Scalpdex total score as observed over time.
- Change and percent change from baseline in Overall Assessment of Erythema score
- Change and percent change from baseline in Overall Assessment of Scaling score
- Achievement of an Overall Assessment of Erythema (0-3 scale) score of 0 or 1 plus a 2-grade improvement from Baseline as observed over time.
- Achievement of an Overall Assessment of Scaling (0-3 scale) score of 0 or 1 plus a 2-grade improvement from Baseline as observed over time.
- Achievement of an Overall Assessment of Erythema (0-3 scale) score of 0 as observed over time.
- Achievement of an Overall Assessment of Scaling (0-3 scale) score of 0 as observed over time.

- Change and percent change from baseline in % body surface area (BSA) affected by disease as observed over time.
- Change and percent change in Worst Itch – Numeric Rating Score (WI-NRS) as observed over time.
- In subjects with a Baseline WI-NRS pruritus score of ≥ 4 , achievement of a ≥ 4 -point improvement from Baseline in WI-NRS pruritus score as observed over time.
- Achievement of Itch-free state which is defined as post-baseline WI-NRS of 0 or 1

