3.1. Overall Design

This is an open-label, single-arm, long-term 52-week safety study of subjects with seborrheic dermatitis. This study will include both male and female subjects 9 years and older. Subjects rolling over from ARQ-154-116 (Cohort 1 Group 2) will not be summarized in the tables and would be listed only.

Cohort 1: This includes subjects of age 9 years or older from ARQ-154-203 and ARQ-154-116 studies and rolled into this extension study on the final visit from previous study. Subjects rolling over from ARQ-154-203 and ARQ-154-116 are separated into groups as indicated below.

Group 1: Subjects rolled over from ARQ-154-203 without gap

Group 2: Subjects rolled over from ARQ-154-116 (listings only and will not appear in summary tables)

Cohort 2: This includes subjects of age 12 years or older who may or may not have participated in a prior ARQ-154 study. The subjects could be either de novo subjects (requiring an IGA of disease severity of at least Moderate [“3”] at Baseline) or subjects who completed an ARQ-154 study before the initiation of this study (any IGA at Day 1 of this

study is allowed). Subjects in Cohort 2 are separated into groups as indicated below:

Group 3: Subjects rolled over from ARQ-154-203 with gap

Group 4: De novo subjects

Subjects will apply study drug once a day for up to 52 weeks. Subjects in both Cohorts cannot have more than 20% BSA affected by disease. All lesions on a subject will be treated including the scalp, face, trunk, and intertriginous areas.

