- ^c IGA will be a 5-point scale ranging from completely clear (0) to severe (4). IGA should be completed prior to other physician assessments. Overall assessment of erythema (0-3 scale) and overall assessment of scaling (0-3 scale) will be completed. Total BSA affected by seborrheic dermatitis will be determined at each visit. A body diagram should be used to record areas of seborrheic dermatitis involvement.
- ^d Adolescents and adults will complete the C-SSRS (12 years of age and older). Adults will complete the PHQ-8. Adolescents (ages 12 -17, inclusive) will complete the modified PHQ-A. Parents/caregivers will complete CDI-2 (parent report) for children 9-11 years of age, inclusive.
- ^e A pregnancy test will be administered to all females of child-bearing potential. A serum pregnancy test will be performed at the Screening visit only for Cohort 2. A urine pregnancy test will be performed at Day 1, Weeks 4, 12, 24, 36 and 52. A negative result is required for continued participation in the study, and results must be available prior to dispensing of IP at each visit.
- ^f Local tolerability will be assessed prior to IP application in the clinic for the Investigator assessment of skin (Berger and Bowman skin irritation score) and 10-15 minutes post IP application for the subject's "0-3" burning/stinging assessment at Baseline. Note for Investigator tolerability assessments: **reactions at the site of product application, which may occur post-Baseline, should be differentiated from the preexisting inflammation associated with the subject's seborrheic dermatitis.** At Weeks 4, 12, 24, 36, and 52 will be a recall assessment of burning/stinging experienced post drug application on the previous day of the clinic visit.
- ^g An assessment for hypopigmentation and hyperpigmentation will be performed by the investigator at all clinic visits.
- ^h At selected sites, medical photography will be obtained for target lesions. All efforts will be made to de-identify the subjects. Subjects who are unwilling to participate in the medical photography will be allowed to opt out of this procedure.
- ⁱ Kits will be dispensed based on %BSA affected. See IP Handling Manual for details.
- ^j Any emergent AEs will be followed in the clinic for up to one month at the Investigator's discretion until resolved or otherwise judged as clinically stable.

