6.1.6. Subgroup

The subgroup analyses of selected safety and efficacy endpoints will be based on the below subgroup variables at both primary baseline and OLE baseline:

- Age groups (9-11 years, 12-17 years, 18-64 years, and ≥ 65 years)
- Gender (Male vs. Female)
- Race (White, Black vs. Other)
- Ethnicity (Hispanic vs. Non-hispanic)
- Baseline IGA (3 vs. 4 for primary baseline, 0 or 1 vs. 2 vs. 3. vs. 4 for OLE baseline)
- Baseline BSA% ($<5\%$ vs. $\geq 5\%$)
- Baseline BSA% tertiles based on overall group

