- **PHQ-8** = sum of the 8 questions (individual questions scored as Not at all=0, Several days=1, More than half the days=2, and Nearly every day=3; range for score 0 to 24). If more than 1 item is missing the score should not be calculated. If 1 item is missing the score is calculated as (sum of answered items*8)/number of answered items.
- **PHQ-A** = sum of the 8 questions (individual questions scored as Not at all=0, Several days=1, More than half the days=2, and Nearly every day=3, (range for score 0 to 24). If more than 1 item is missing, the score should not be calculated. If 1 item is missing, the score is calculated as (sum of answered items*8)/number of answered items.
- **CDI-2** = total score is calculated as a sum of the 17 questions (individual questions scored as much or most of the time=3, often=2, some of the time=1, Not at all=0; range for score 0 to 51).
 - CDI-2 emotional problem scale is a sum of 9 questions (Q1, Q3-6, Q8, Q10 -12)
 - CDI-2 function problem scale is a sum of 8 questions (Q2, Q7, Q9, Q13-17)
- **Scalpdex score transformation** = Scalpdex is rated on a 1 to 5 scale which will be transformed to 0 to 100 Scale where 1=0; 2=25; 3=50; 4=75; 5=100. This transformed score is used to calculate scale scores.
- **Scalpdex Emotions Scale** = average of (Q2, Q4, Q5, Q6, Q7, Q9, Q10, Q11, Q12, Q14, Q16, Q17, Q19, Q20, Q22) after transforming to 0 to 100 scale as mentioned above.

Q refers to question number. Q19 will be reverse scored i.e., 1=100; 2=75; 3=50; 4=25; 5=0.

- **Scalpdex Symptoms Scale** = average of (Q1, Q3, Q8) after transforming to 0 to 100 scale as mentioned above. Q refers to question number.
- **Scalpdex Functioning Scale** = average of (Q13, Q15, Q18, Q21, Q23) after transforming to 0 to 100 scale as mentioned above. Q refers to question number.
- **Scalpdex Total Score** = calculated as mean of all the 23 scalpdex questions using the transformed scale of 0 to 100. Q19 will be reverse scored i.e., 1=100; 2=75; 3=50; 4=25; 5=0 while calculating the mean. Q refers to question number.
- **Total % BSA (body surface area)** = sum of coverage areas of head, limbs, upper limbs, and lower limbs.
- **Change from baseline** = value at current time point – value at baseline. This is derived separately for primary baseline and OLE baseline.
- **Percent change from baseline** = (value at current time point – value at baseline)/value at baseline. This is derived separately for primary baseline and OLE baseline.

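### The SAP's formula for total %BSA leaves out the trunk and lists the limbs twice, so BSA results are wrong if it is programmed as written

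*SAP*

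**What the plan says.** SAP section 6.1.7 (Derived Variables) gives the rule for total %BSA: "sum of coverage areas of head, limbs, upper limbs, and lower limbs".

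The trunk is in scope in both documents. The protocol's inclusion criteria for Cohort 2 (section 5.4.1) require "Seborrheic dermatitis of the scalp and/or face and/or trunk and/or intertriginous areas", up to the 20% limit. SAP section 3.1 says "All lesions on a subject will be treated including the scalp, face, trunk, and intertriginous areas", and sets the ceiling: "Subjects in both Cohorts cannot have more than 20% BSA affected by disease".

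The quantity wanted is the whole affected area. The footnote to the schedule in SAP section 3.7 reads "Total BSA affected by seborrheic dermatitis will be determined at each visit". Protocol section 6.2.4 describes the hand method of measurement, with one hand taken as 1%, but gives no regional breakdown or summation rule.

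The derived total is used in three places:
- an other secondary efficacy endpoint, "Change and percent change from baseline in % body surface area (BSA) affected by disease as observed over time" (SAP 2.2.1.3, analysed in 8.3);
- the baseline characteristics table (SAP 7.2);
- two subgroup factors in SAP 6.1.6, a cut at 5% and "Baseline BSA% tertiles based on overall group".

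**The concern.** A total over body regions needs regions that do not overlap and that together cover the body. This list fails on both counts: no term holds trunk disease, and the general limb term repeats the two specific ones. Section 6.1.7 is the text from which the analysis datasets are programmed, so the wording is operative.

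If it were followed, subjects with trunk involvement would have too low a total and subjects with limb involvement too high a total. Change and percent change in %BSA would then not describe the course of the whole disease. The baseline table would misstate its extent, and the BSA subgroups would contain the wrong subjects. Those subgroups reach beyond the BSA table: SAP 8.2.1 applies the 6.1.6 subgroups to the IGA analyses, and SAP section 10 adds subgroup tables for TEAEs by severity.

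**Working it through.** The plan states no numerical result for this derivation, so there is no figure to reproduce. The check compares the formula as written with a proper partition of the body.

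**Inputs.** The formula comes from SAP 6.1.7, the 20% limit from SAP 3.1 and the 5% cut from SAP 6.1.6. The documents give no regional %BSA values, so every regional profile below is an assumption chosen to show direction and range.

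**Notation.** H = head, T = trunk, U = upper limbs, Lo = lower limbs, each as % of total BSA.

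**Formulas.**
- As written, with the general limb term equal to U + Lo: H + (U + Lo) + U + Lo = H + 2(U + Lo).
- Partition: H + T + U + Lo.
- Error = as written minus partition = (U + Lo) - T.

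| Assumed profile (%) | Partition | As written | Error | 5% subgroup |
|---|---|---|---|---|
| H 3 | 3 | 3 | 0 | unchanged |
| H 2, T 4 | 6 | 2 | -4 | moves to <5% |
| H 2, T 3.5 | 5.5 | 2 | -3.5 | moves to <5% |
| H 2, U + Lo = 2 | 4 | 6 | +2 | moves to ≥5% |
| H 2, U 1, Lo 0.5 | 3.5 | 5.0 | +1.5 | moves to ≥5% |
| H 3, T 4, U 1 | 8 | 5 | -3 | unchanged |
| T 20 | 20 | 0 | -20 | moves to <5% |
| U 10, Lo 10 | 20 | 40 | +20 | unchanged |

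The last two rows are the bounds at the entry limit. The 40% in the last row could not be a true value for an eligible subject at entry. The error is zero when disease is on the head only, or when limb and trunk areas happen to be equal.

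**Percent change.** Assume head disease falls from 3% to 0.5% while trunk disease stays at 4%.
- Partition: (4.5 - 7)/7 = -35.7%.
- As written: (0.5 - 3)/3 = -83.3%.

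With trunk-only disease the baseline as written is 0, and percent change is undefined because SAP 6.1.7 divides by the baseline value.

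**If the eCRF has no combined limb field.** The formula then reduces to H + U + Lo, and the error is -T. The double count disappears but the trunk is still lost: H 2, T 4 still scores 2% instead of 6%.

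**Search for a correction elsewhere.** Protocol 6.2.4 has no regional formula, the schedule footnotes refer only to a total, and SAP section 10 lists no change to the BSA derivation.

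**The case against.** The best case against giving this weight is that it is a one-word slip with unproven consequences. The list reads naturally as four regions with the wrong word in second place, and putting the trunk there removes both faults at once. The double count needs a combined limb field on the eCRF, which the documents do not show. If sites record a single total, the formula has no effect. A programmer who finds no such field would have to go back to the data collection documents, which the SAP names as reference material. Limbs are not among the named disease sites, so the over-counting cases may be rare. The endpoint is descriptive and ranks as other secondary, only selected endpoints are analysed by subgroup, and no decision rule uses derived BSA.

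Most of this stands as a limit on impact. The slip is the likeliest explanation, though nothing in the documents confirms it. The size in the actual data is unknown, and the limb examples are less firmly grounded than the trunk ones.

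It does not rescue the text. The trunk is a named site and is missing whichever way the limb term is read. If programmers silently substitute the right region, the analysis departs from the approved plan without a record; if they do not, the totals are wrong. Either way the line needs correcting.

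**Conclusion.** The derivation is wrong as written. Taken literally, each subject's total is off by the limb area minus the trunk area. That is anywhere from -20 to +20 points at the entry limit, and enough to move subjects across the 5% cut in both directions.

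This rests on three assumptions: that the eCRF collects areas by region, that the formula is programmed literally, and, for the over-count only, that a combined limb value enters the sum. If the eCRF records one total, the numerical effect is nil and only the text is at fault. The share of subjects with trunk or limb disease is not given, so the effect on group summaries cannot be estimated.

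The overall TEAE and SAE summaries do not depend on BSA; only displays by BSA subgroup would be affected. This should be corrected, but it does not threaten the study's main conclusions.

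**What to change.** Replace the line in SAP 6.1.7 with a sum over the non-overlapping regions on the eCRF, each counted once. If those are the usual four, this is: total %BSA = head (including scalp and face) + trunk + upper limbs + lower limbs. State the region to which intertriginous areas are assigned, since they are a named disease site. If the eCRF records a single total, say that this value is used directly and delete the sum.

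The cost is one line of SAP text and a check against the annotated CRF. Data collection does not change. If the derivation has already been programmed, confirm which version was used, and rerun the BSA tables and BSA subgroup displays if it followed the printed formula.

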5.6.3. Treatment Administration

Seborrheic dermatitis lesions that have completely resolved, in the opinion of the Investigator, do not require continued treatment. At every clinic visit the Investigator will determine if the IGA are considered ‘clear’ and the subject will stop applying the investigational product. The subject will contact the clinical study site and document in diary when seborrheic dermatitis returns prior to restarting investigational product. Subjects that clear between scheduled visits should return for an unscheduled visit for the Investigator to confirm IGA score are considered ‘clear’.

Unless otherwise instructed by the Investigator, subjects will apply investigational product once daily. At the Day 1 visit, the study staff will demonstrate to the subject how to apply ARQ-154 foam using the first Can from the Kit that is provided to the subject at Day 1. Study site staff will be trained to ensure a proper amount is dispensed from the foam Can and applied to seborrheic dermatitis lesion(s) as a thin layer and rubbed in thoroughly but gently, until the foam has disappeared. **For scalp lesions, special attention should be given to ensuring adequate investigational product is applied to scalp skin and not rubbed off on hair.** The subject will then practice dispensing a similar amount of investigational product and applying to seborrheic dermatitis lesion(s). The study staff will confirm that the subject’s application technique is correct. Cohort 1 Group 2 subjects will apply the last dose of IP for ARQ-154-116 Week 2 (Day 15) study visit; subjects will enroll in ARQ-154-214 on the same day but will start applying IP the following day (Day 2). The study staff will review with the subject the appropriate IP

dispensing and application technique for the ARQ-154-214 study during the Baseline visit (Day 1).

IP will be applied in the evening to areas of lesions of seborrheic dermatitis. IP will be applied at least 20 minutes before going to bed.

For Scalp Lesions: IP will be applied when the skin and hair on the scalp is dry. Subjects should dispense IP on their fingers, then part hair where there are lesions and rub IP into scalp skin. As the IP is applied, the subject should move any hair away to ensure that sufficient foam is actually applied directly to the affected skin on the scalp. Subjects should not use other hair products for at least an hour before or after application.

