6.6. Adverse Events

6.6.1. Adverse Event Definition

An AE means any untoward medical occurrence associated with the use of a drug in humans, whether or not considered drug related. An AE can therefore be any unfavorable and unintended sign (including an abnormal laboratory finding), symptom, or disease temporally associated with the use of a medicinal (investigational) product, whether or not related to the medicinal (investigational) product.

AEs will be collected following informed consent of the subject through subject study completion.

A treatment emergent adverse event (TEAE) is defined as an AE that started post application of IP at the Day 1 visit through study completion.

Application site reactions will be considered adverse events if they require intervention, suspension or discontinuation of IP.

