7.2.1. Adverse Events

All treatment-emergent AEs occurring during the study will be recorded and classified on the basis of MedDRA terminology for the safety population. Treatment-emergent AEs are those AEs with an onset on or after the first date of study treatment in this study. All treatment-emergent AEs will be summarized by treatment group, the number of subjects reporting treatment-emergent AEs, system organ class, preferred term, severity, relationship, and seriousness.

Serious adverse events (SAEs) will be listed by subject. SAEs will be summarized by treatment group, severity, and relationship to study treatment.

For AEs, each subject will be counted only once within a system organ class or a preferred term using the event with the greatest relationship and greatest severity.

All information pertaining to AEs noted during the study will be listed by subject, detailing the verbatim description given by the Investigator, preferred term, system organ class, start date, stop date, severity, action taken regarding IP, corrective treatment, outcome, and drug relatedness. The event onset will also be shown relative (in number of days) to date of first application. In addition, a listing of subjects who prematurely discontinue from the IP due to adverse events will also be provided.

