6.1. Statistical Definitions and Algorithms

6.1.1. Baseline

There are three baseline definitions for the analyses:

- Primary baseline is defined as the last observation before the first dose of roflumilast foam 0.3% in either ARQ-154 parent study or this study for subjects administered vehicle previously.
- Open-label baseline (OLE baseline) is defined the last observation before the first dose of roflumilast foam 0.3% in this study. For subjects in Cohort 1 who choose to enroll in this study, study procedures will not be repeated; study sites will carry over the information from the prior ARQ-154 study to the Day 1 visit for this study. For subjects in Cohort 2 Group 4, the definition for Primary and OLE baseline is the same.
- Safety baseline is defined as primary baseline for Cohort 1 Group 1, and OLE baseline for Cohort 2 Group 3 and Group 4.

The following table described the baseline used in the analysis:

Cohort Groups	Prior therapy, medical history	Demog and Efficacy Analysis	Safety Analysis for AE, PHQ8, PHQ-A, Prior and Concomitant medications	Safety Analysis for lab, vital signs and tolerability assessments
Cohort 1 Group 1	OLE baseline	Primary baseline and OLE baseline	OLE baseline	Primary baseline
Cohort 2 Group 3	OLE baseline	Primary baseline and OLE baseline	OLE baseline	OLE baseline
Cohort 2 Group 4	OLE baseline	Primary baseline and OLE baseline	OLE baseline	OLE baseline
Cohort 2 Total	OLE baseline	Primary baseline and OLE baseline	OLE baseline	OLE baseline

Overall	OLE baseline	Primary baseline and OLE baseline	OLE baseline	Safety baseline of roflumilast foam 0.3% in this study for subjects in the safety analysis population. For subjects in Cohort 2 Group 4, the definition for Primary and OLE Baselines is the same
----------------	--------------	-----------------------------------	--------------	---

Baseline values will most commonly be from Day 1.

For subject tolerability assessments, baseline is derived as the last non-missing measurement taken on the day of first application of study drug.

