- **TEAE** = any AE that started after application of IP at the Baseline Visit in this extension study, or in parent study through completion.
- **C-SSRS Suicidal Ideation** = A “yes” answer at any time during treatment to any one of the five suicidal ideation questions (Categories 1-5: Wish to be Dead, Non-specific Active Suicidal Thoughts, Active Suicidal Ideation with Any Methods (Not Plan) without Intent to Act, Active Suicidal Ideation with Some Intent to Act, without Specific Plan Active Suicidal Ideation with Specific Plan and Intent).
- **C-SSRS Suicidal Behavior** = A “yes” answer at any time during treatment to any one of the five suicidal behavior questions (Categories 6-10: Preparatory Acts or Behavior, Aborted Attempt, Interrupted Attempt, Actual Attempt (non-fatal), Completed Suicide).

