9.1. Adverse Events

All AEs will be coded using the MedDRA dictionary version 24.1 or above.

A TEAE is defined as an AE that started after application of IP at the Baseline Visit in this extension study. All TEAEs will be summarized from OLE baseline.

An overall summary of TEAEs will be provided; this will present number and percent of subjects who reported at least 1: TEAE (including all TEAEs, TEAEs by maximum severity, and TEAEs by greatest relationship), treatment emergent SAE (TESAE), TEAE leading to study drug withdrawal, TEAE leading to study withdrawal, or TEAE resulting in death.

The number and percent of subjects reporting TEAEs, grouped by MedDRA system organ class (SOC) and preferred term (PT), will be tabulated by all TEAEs, non-serious TEAEs, maximum severity, or greatest relationship to study IP; Cohort and by groups and overall. In the case of multiple occurrences of the same TEAE within the same subject, each subject will only be counted once for each preferred term.

The number and percent of subjects reporting TEAEs will be tabulated by PT and presented by groups and overall.

In the summaries showing severity and relationship to study medication, the event with the maximum severity (mild < moderate < severe) or strongest relationship (not related < related) will be reported. If a particular event is missing the severity and/or relationship, then the strongest possible severity or relationship will be assumed for analysis (severity = severe, relationship = likely).

All the AEs will be listed. The AEs that are treatment emergent will be flagged. Any AEs related to the application site will be flagged in the listing.

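### SAP 6.1.7 counts parent-study events as treatment-emergent, against SAP 9.1 and the protocol; separately, the primary AE endpoints get only crude percentages although follow-up was lengthened mid-study

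*SAP*

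**What the plan says.** Protocol 4.2.1 names two primary analyses: occurrence of TEAEs and occurrence of SAEs. Treatment emergence is then described in five places:

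- SAP 6.1.7, the list of derived variables: "any AE that started after application of IP at the Baseline Visit in this extension study, or in parent study through completion".
- SAP 9.1, the AE analysis: "A TEAE is defined as an AE that started after application of IP at the Baseline Visit in this extension study", followed by "All TEAEs will be summarized from OLE baseline". For the listings it adds "The AEs that are treatment emergent will be flagged".
- SAP 6.1.1, baseline table: the column headed "Safety Analysis for AE, PHQ8, PHQ-A, Prior and Concomitant medications" gives OLE baseline in every row.
- Protocol 6.6.1: "an AE that started post application of IP at the Day 1 visit through study completion".
- Protocol 7.2.1: "Treatment-emergent AEs are those AEs with an onset on or after the first date of study treatment in this study".

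SAP Section 10 lists the departures from the planned analysis; none concerns the TEAE definition. Under protocol 5.6.3, Cohort 1 Group 2 applies its last ARQ-154-116 dose on the day it enrols and first applies product for this study on Day 2. SAP 4.2 reports that group in listings only.

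On the summary measure, SAP 9.1 to 9.1.2 plans numbers and percentages of subjects, and SAP 4.1 sets the general denominator as all subjects in the population. The protocol's Summary of Changes records that Amendment 1 added contacts at Weeks 30, 36, 44 and 52 and lengthened treatment to as much as 52 weeks. SAP 7.6 gives a separate exposure and compliance summary for subjects who finished or left before that amendment. No AE summary does the same.

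**The concern.** Section 6.1.7 is where a programmer looks for the rule that sets the TEAE flag. Read literally, it pulls in events that began in the parent study. It refers to IP and not to roflumilast, so for former vehicle subjects it also covers events that began on vehicle. De novo subjects have no parent study, so the counting window would differ between groups inside one table. For Cohort 1 Group 2 the listing flag is the only place where the definition appears, so no table would correct it.

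The second issue is one of analysis choice, not contradiction. The objective is safety over 52 weeks. If some subjects were planned for a shorter period, a percentage over all treated subjects estimates neither the 24-week nor the 52-week risk, and exposure tables alone do not show how far off it is.

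**Working it through.** **The definitions side by side.** Four of the five passages start the clock in this study; only SAP 6.1.7 adds the parent study. Protocol 7.1.1 does use baselines that reach back into the parent study, but it sends the reader to 7.2.1 for treatment emergence, and 7.2.1 is limited to this study. The intended tables are therefore extension-only, and 6.1.7 is the outlier.

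The Baseline Visit anchor in SAP 6.1.7 and 9.1 also fails for Cohort 1 Group 2. The product applied that day is the last parent-study dose, and treatment in this study begins the next day. Protocol 7.2.1, which uses the first treatment date in this study, handles this correctly.

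**Inputs.** The plan gives no AE rate, so there is no figure to reproduce. From the documents: SAP Table 2 target days (85, 141, 225, 309, 421) minus Table 3 target days (29, 85, 169, 253, 365) give 56 days at every visit, which is the eight-week parent study. Assumed: a 52-week risk R of 30% for TEAEs and 2% for SAEs, the share of rollover subjects, and the share f with 24 weeks of planned follow-up. The 24 weeks is inferred: it is the last visit left once those added by Amendment 1 are removed, and protocol 7.3.1 and 7.3.2 still stop there.

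**Effect of the definition.** At Week 52 the 6.1.7 window is 421/365 = 1.153 times the 9.1 window (15.3% longer). At Week 24 it is 225/169 = 1.331 times (33.1% longer).

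With constant hazard, H = −ln(1 − R) over 364 days. For R = 0.30, H = 0.3567.

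- Risk over 364 + 56 = 420 days: 1 − exp(−0.3567 × 420/364) = 33.7%.
- Increase for a rollover subject: 33.74 − 30.00 = 3.74 points.
- Increase in the Overall column with 25%, 50% or 75% rollovers: 0.9, 1.9 or 2.8 points.

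**Effect of unequal follow-up.** Let p24 be the risk by day 168. The crude figure falls short of the 52-week risk by f × (R − p24).

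- Constant hazard, R = 0.30: p24 = 1 − exp(−0.3567 × 168/364) = 15.18%.
- Front-loaded, R = 0.30, half of H in the first 56 days and the rest spread evenly over 308 days: the hazard by day 168 is 0.1783 + 0.1783 × 112/308 = 0.2432, so p24 = 21.59%.
- Constant hazard, R = 0.02: p24 = 0.93%.

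| Shortfall in points | f = 5% | f = 10% | f = 25% | f = 50% |
|---|---|---|---|---|
| R = 30%, constant hazard | 0.7 | 1.5 | 3.7 | 7.4 |
| R = 30%, front-loaded | 0.4 | 0.8 | 2.1 | 4.2 |
| R = 2%, constant hazard | 0.05 | 0.11 | 0.27 | 0.54 |
| All first events by Week 24 | 0 | 0 | 0 | 0 |

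The first effect raises the crude figure and the second lowers it, so they can partly cancel.

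**The case against.** On the definition, SAP 9.1 governs the AE tables and mentions the listing flag in the same section, so a careful programmer would follow it. The added points above would then never appear in a table. AEs here are collected from consent, which Cohort 1 signs after the parent study's final visit, and nothing says that parent-study AEs are pooled for Groups 1 and 3. Group 2 is about ten subjects, and protocol 7.2.1 requires its listings to show onset relative to first application. All this lowers the chance of a wrong count. It does not remove the contradiction: 6.1.7 still instructs otherwise, Table 2 windows parent-study visits for analysis, and ARQ-154-116 information goes into the Group 2 listings.

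On follow-up, the endpoint is occurrence, the study is descriptive, and neither document names a 52-week cumulative incidence as its target. The 24 weeks is inferred. Protocol 7.1 waits until all treated Group 1 and Cohort 2 subjects could have reached Week 52, which makes the 25% and 50% scenarios less likely. SAP 7.6 will show readers how long subjects were treated. These points limit the size and make this an improvement, not an error. They do not remove it, since the SAP itself expects subjects who completed or discontinued before the extension. It is also fair that patient-years must be defined, because subjects pause product when clear.

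**Conclusion.** Both parts hold, with different weight. The TEAE wording in SAP 6.1.7 is wrong as written: it conflicts with SAP 9.1, the AE baseline rule and two protocol sections on a primary endpoint. This rests on the text alone and needs no assumption. Its numerical effect is nil if programmers follow 9.1. If they follow 6.1.7 and parent-study AEs are in the data, it is about 0.9 to 2.8 points in the Overall column, at an assumed 30% risk, constant hazard and 25% to 75% rollovers.

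The lack of any time-adjusted AE summary is a weakness that is cheap to repair. At the same 30% risk the shortfall runs from zero to 7.4 points, depending on when first events occur and on a share of short follow-up that the documents do not give. The upper end is unlikely given the planned timing of the final analysis.

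**What to change.** 1. In SAP 6.1.7, remove the reference to the parent study. Use one definition there and in 9.1: an AE with onset on or after the first application of roflumilast foam 0.3% in this study, through study completion. For Cohort 1 Group 2 that application is on Day 2, as protocol 5.6.3 states. On-or-after follows protocol 7.2.1, so the wording in 9.1, which says after, must change with it.
2. If a view of all active exposure is wanted, give it as a separately labelled table counted from the first roflumilast dose and excluding vehicle-period events.
3. Beside the crude counts of TEAEs and SAEs, report subjects with a first event per 100 patient-years at risk, and Kaplan-Meier cumulative incidence at Weeks 24 and 52. Censor event-free subjects at the end of AE collection. State that time at risk runs from first application to first event or censoring and includes time off product after clearing, to match the TEAE definition. If first events cluster early, rely on the Kaplan-Meier figures, because a single rate averages over a changing hazard.

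The cost is a short edit to two SAP sections and one or two extra tables from dates already collected. The 52-week estimate may be somewhat higher than the crude percentage, and it will be less precise if few subjects remain at risk at Week 52.
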